10.1 General Considerations

Safety parameters will be evaluated for the safety analysis set.

10.2 Adverse Events

Adverse events will be coded using MedDRA version 20.0.

Adverse events are grouped according to start of IMP as follows:

- Pre-treatment adverse event, i.e. any adverse event occurring after signed informed consent and before start of IMP, or a pre-existing medical condition that worsens in intensity after signed informed consent but before start of IMP.
- Treatment-emergent adverse event, i.e. any adverse event occurring after start of IMP and before the end-of-trial visit, or a pre-treatment adverse event or pre-existing medical condition that worsens in intensity after start of IMP and before the end-of-trial visit.

Treatment-emergent adverse events will be presented in summary tables and listings. Pre-treatment adverse events will be presented in a listing only.

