6.8 End-of-Trial

Subjects who have a positive β hCG test and continue to the clinical pregnancy visit will have end-of-trial assessments done at that visit. Subjects who have a negative β hCG test will proceed directly to end-of-trial assessments. Subjects experiencing a full menstrual bleeding following transfer can also proceed to the end-of-trial visit and have the β hCG test performed as part of the end-of-trial assessments, if this occurs 7-15 days after transfer.

The following must take place at the end-of-trial visit:

- Body measurements (body weight)
- Physical examination
- Gynaecological examination
- Vital signs
- Blood collection for central laboratory analysis of clinical chemistry and haematology parameters
- Drug accountability, if applicable
- Recording of use of any concomitant medication
- Recording of adverse events
- Completion of end-of-trial form

These assessments serve to document the subject's physical health at the end of the trial.

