7.4.7 Physical Examination

A complete physical examination will be performed at screening and end-of-trial. Information will be recorded for general appearance, central and peripheral nervous system, head and neck (including ears, eyes, nose, mouth and throat), respiratory system, cardiovascular system, gastrointestinal system, lymphatic system, urinary system, musculoskeletal system and skin.

At screening, each category will be evaluated as normal, abnormal not clinically significant or abnormal clinically significant. Abnormal clinically significant findings at screening must be reported on the Medical History Log.

At end-of-trial, potential changes from screening to end-of-trial will be evaluated for each category. In case of changes, these will be evaluated as normal, abnormal not clinically significant or abnormal clinically significant. Abnormal clinically significant changes from screening to end-of-trial must be recorded as adverse events.

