8.2.2 Recording of Adverse Events

The investigator must record all adverse events in the Adverse Event Log provided in each subject's eCRF with information about:

- Adverse event
- Date and time of onset
- Intensity
- Causal relationship to IMP
- Action taken to IMP
- Other action taken
- Date and time of outcome
- Outcome
- Seriousness

Each of the items in the Adverse Event Log is described in detail in the following sections.

Adverse Event

Adverse events should be recorded as diagnoses, if available. If not, separate signs and symptoms should be recorded. One diagnosis/symptom should be entered per record.

If a subject suffers from the same adverse event more than once and the subject recovers in between the events, the adverse events should be recorded separately. If an adverse event changes in intensity, a worst-case approach should be used when recording the event, i.e. the highest intensity and the longest duration of the event.^d

Note: A procedure is not an adverse event; the reason for conducting the procedure is. Hospitalisation is not an adverse event; the reason for hospitalisation is. Death is not an adverse event, but the cause of death is (an exception is sudden death of unknown cause, which is an adverse event).

^d Exception: if an adverse event with onset before the first IMP administration (i.e. a pre-treatment adverse event) worsens in intensity, this must be recorded as two separate events. The initial adverse event should be recorded with outcome "not recovered" and the date and time of outcome is when the intensity changed. The second adverse event should be recorded with date and time of onset when the intensity changed.

Date and Time of Onset

The date of onset is the date when the first sign(s) or symptom(s) were first noted. If the adverse event is an abnormal clinically significant laboratory test or outcome of an examination, the onset date is the date the sample was taken or the examination was performed.

Intensity

The intensity of an adverse event must be classified using the following 3-point scale:

- Mild: Awareness of signs or symptoms, but no disruption of usual activity.
Moderate: Event sufficient to affect usual activity (disturbing).
Severe: Inability to work or perform usual activities (unacceptable).

Causal Relationship to IMP

The possibility of whether the IMP caused the adverse event must be classified as one of the following:

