- Pre-treatment adverse event, i.e. any adverse event occurring after signed informed consent and before start of IMP, or a pre-existing medical condition that worsens in intensity after signed informed consent but before start of IMP.
- Treatment-emergent adverse event, i.e. any adverse event occurring after start of IMP and before the end-of-trial visit, or a pre-treatment adverse event or pre-existing medical condition that worsens in intensity after start of IMP and before the end-of-trial visit.

Treatment-emergent adverse events will be presented in summary tables and listings. Pre-treatment adverse events will be presented in a listing only.

A treatment-emergent adverse event overview table will be prepared including the number of subjects reporting an adverse event, the percentage of subjects with an adverse event, and the number of events reported, for the following categories: all adverse events, severe adverse events, adverse reactions, adverse events leading to discontinuation, serious adverse events and deaths. An adverse reaction is an adverse event judged by the investigator to be related to IMP with a reasonable possibility.

Treatment-emergent adverse events will be tabulated by system organ class (SOC) alphabetically and preferred term (PT) in decreasing order of frequency. The following will be presented: number of subjects reporting an adverse event, the percentage of subjects with an adverse event, and the number of events reported.

Summary tables will be produced for the following: all adverse events, adverse events by causality (reasonable possibility / no reasonable possibility), adverse events leading to death, adverse events by intensity (mild / moderate / severe), adverse reactions by intensity (mild / moderate / severe), serious adverse events, adverse events leading to discontinuation, adverse events with an incidence of $\geq 5\%$ in any treatment group, and non-serious adverse events with an incidence of $\geq 5\%$ in any treatment group.

Clinical Chemistry and Haematology Parameters

Safety laboratory variables will be grouped under “Haematology” and “Clinical Chemistry”.

The baseline is based on the blood sample drawn at screening. Treatment-emergent laboratory data will be obtained at end-of-stimulation and end-of-trial.

The circulating levels of clinical chemistry and haematology parameters including change from baseline will be tabulated for each time-point for each laboratory variable.

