10.2.2 Incidence of Adverse Events

Treatment-emergent adverse events will be tabulated by system organ class (SOC) alphabetically and preferred term (PT) in decreasing order of frequency. The following will be presented: number of subjects reporting an adverse event, the percentage of subjects with an adverse event, and the number of events reported.

Summary tables will be produced for the following: all adverse events, adverse events by causality (reasonable possibility / no reasonable possibility), adverse events leading to death, adverse events by intensity (mild / moderate / severe), adverse reactions by intensity (mild / moderate / severe), serious adverse events, adverse events leading to discontinuation, adverse events with an incidence of $\geq 2\%$ in any treatment group, and non-serious adverse events with an incidence of $\geq 2\%$ in any treatment group.

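### The treatment-emergent AE window closes before the end-of-trial visit, so AEs dated by that visit's own assessments miss the tables of SAP 10.2.1 and 10.2.2

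*SAP*

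**What the plan says.** SAP 10.2 sorts AEs into two classes by reference to the start of IMP. Pre-treatment AEs fall between consent and first IMP. The other class is defined as: "Treatment-emergent adverse event, i.e. any adverse event occurring after start of IMP and before the end-of-trial visit". A second half of the definition covers earlier conditions that worsen, with the same closing limit. Protocol 9.7.4 carries the identical limit: "any adverse event occurring after start of IMP and before the end-of-trial visit".

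The class decides where an AE is reported: "Treatment-emergent adverse events will be presented in summary tables and listings. Pre-treatment adverse events will be presented in a listing only". The overview table (SAP 10.2.1) is headed as treatment-emergent, and SAP 10.2.2 says of the incidence tables: "Treatment-emergent adverse events will be tabulated by system organ class (SOC) alphabetically and preferred term (PT) in decreasing order of frequency". Neither document names a table or listing for an AE that fits neither class.

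Two onset rules stand in protocol 8.2.2. In general: "The date of onset is the date when the first sign(s) or symptom(s) were first noted". For a clinically significant laboratory or examination result, "the onset date is the date the sample was taken or the examination was performed".

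**The concern.** The end-of-trial visit is a full safety assessment, and the AE definition stops just short of it. An AE that comes to light only through that visit's examinations, bloods or scan takes the visit date as its onset. It is then too late to be treatment-emergent and plainly not pre-treatment.

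Comparing the safety profile, including adverse events, is a stated secondary objective (protocol 2.1, SAP 2). A programmer who applies the definition literally would leave these AEs out of the incidence, causality, intensity and seriousness tables. Checking the SAP against the protocol would not reveal this, because the two agree. The events concerned include clinically significant examination or laboratory changes and pregnancy losses first seen on the scan.

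**Working it through.** The documents give no figure to reproduce. The check is to follow one AE through the rules.

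1. **What happens at the visit.** Protocol 6.8 schedules physical and gynaecological examinations, vital signs, safety bloods and AE recording at end-of-trial. Women with a positive βhCG who "continue to the clinical pregnancy visit will have end-of-trial assessments done at that visit" have the pregnancy ultrasound on that occasion too (protocol 6.7). SAP 3.1 confirms that the clinical pregnancy visit is the end-of-trial visit.

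2. **Which findings become AEs.** For the physical examination, protocol 7.4.7 says: "Abnormal clinically significant changes from screening to end-of-trial must be recorded as adverse events". Section 7.4.8 repeats the rule for the gynaecological examination. For laboratory and vital-sign findings the rule is in protocol 8.1, which makes those judged clinically significant AEs. Protocol 8.3.4, under AEs of special interest, defines ectopic pregnancy, spontaneous abortion and biochemical pregnancy wholly or partly by ultrasound.

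3. **What onset they receive.** With no earlier sign or symptom, the second rule of protocol 8.2.2 gives the date of the sample or examination, which is the visit date. I read vital signs and the ultrasound as examinations here.

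4. **Which class they fall in.** Pre-treatment requires onset before IMP, which fails. Treatment-emergent requires occurrence before the visit, which also fails. Recording a time of onset does not help, because the time of an assessment made at the visit is not before the visit.

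5. **Where they are reported as AEs.** The tables of SAP 10.2.1 and 10.2.2 take treatment-emergent AEs only, so these AEs are in none of them.

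6. **Does the rest of the plan use the same cut-off?** No. SAP 10.6 names end-of-trial as one of two time points that supply treatment-emergent laboratory data. SAP 7.3 counts medication as concomitant unless it ended before first IMP or started after the end-of-trial visit, so the visit is inside that window. One blood result could thus be treatment-emergent as a laboratory value and not as an AE.

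7. **Test of the remedy.** If the limit includes the visit, the AE in step 4 meets the treatment-emergent condition and enters the tables.

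**Sensitivity of one table.** SAP 10.2.2 has tables of AEs with incidence of at least 2% in any group. With 328 / 2 = 164 women per arm, assuming all are exposed, 4 / 164 = 2.4% and 3 / 164 = 1.8%. A single omitted subject can therefore move a preferred term below the threshold. This shows what one event can do; it does not estimate how many are lost.

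**The case against.** The best reply is that the wording is loose and no exclusion was planned. The classes are grouped by start of IMP, which suggests that the two were meant to cover everything recorded. AE recording is a listed task at the visit, protocol 7.3.16 has AEs recorded until that visit, and the treatment of laboratory data and medication in step 6 points to an inclusive intent. That may well be right, but neither document says so, and the literal rule is what would be programmed. The same passages also show that the AE limit is out of line with the rest of the plan.

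A reader might infer three stronger things that the documents do not support:

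- **That every AE-related table is affected.** The OHSS tables and analyses in SAP 10.3 time onset from triggering, with no end-of-trial limit. OHSS first found at the last visit would still be counted there.
- **That every AE reported at the last visit is lost.** An AE with earlier signs or symptoms keeps its earlier onset. A pregnancy loss preceded by bleeding or pain may stay in the window.
- **That the findings vanish from the report.** End-of-trial laboratory values, vital signs and examinations have shift tables (SAP 10.6 to 10.9). Ectopic pregnancies and sacs without heart beat show indirectly, as the gap between clinical and vital pregnancy rates. None of these gives AE incidence by preferred term, causality, intensity or seriousness.

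It also stands that the cut-off is the same in both arms and that no differential bias is shown.

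**Conclusion.** The point holds as a defect in the definition. Read literally, AEs whose onset is set by the end-of-trial visit's own examination, blood sample or ultrasound, with no earlier sign or symptom, belong to neither AE class and are left out of the overview and SOC/PT incidence tables. Incidences there would be understated by whatever number of such AEs occurs.

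That number cannot be derived from the documents, which give neither the rate of new findings at the last visit nor the rate of losses first seen on the scan. The conclusion rests on the literal limit and on the second onset rule of protocol 8.2.2. It does not touch the primary analysis or the non-inferiority claim. The correction is worth making because AE comparison is a stated objective and the remedy is small.

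**What to change.** In SAP 10.2 and protocol 9.7.4, change the closing limit of the treatment-emergent definition to read: up to and including the end-of-trial visit (including results of samples taken at that visit). Make the change in both halves, so that it also covers earlier conditions found at that visit to have worsened. The bracketed words are needed because the results may return after the visit day.

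The cost is one phrase in each document and one derivation in the AE dataset. No new data are needed. The only downside is slightly higher AE counts.

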10.2.1 Overview of Treatment-Emergent Adverse Events

A treatment-emergent adverse event overview table will be prepared including the number of subjects reporting an adverse event, the percentage of subjects with an adverse event, and the number of events reported, for the following categories: all adverse events, severe adverse events, adverse drug reactions, adverse events leading to discontinuation, serious adverse events and deaths. An adverse reaction is an adverse event judged by the investigator to be related to IMP with a reasonable possibility.

10.2.2 Incidence of Adverse Events

Treatment-emergent adverse events will be tabulated by system organ class (SOC) alphabetically and preferred term (PT) in decreasing order of frequency. The following will be presented: number of subjects reporting an adverse event, the percentage of subjects with an adverse event, and the number of events reported.

Summary tables will be produced for the following: all adverse events, adverse events by causality (reasonable possibility / no reasonable possibility), adverse events leading to death, adverse events by intensity (mild / moderate / severe), adverse reactions by intensity (mild / moderate / severe), serious adverse events, adverse events leading to discontinuation, adverse events with an incidence of $\geq 2\%$ in any treatment group, and non-serious adverse events with an incidence of $\geq 2\%$ in any treatment group.

10.3 OHSS

Early OHSS (Including OHSS of Moderate/Severe Grade) and/or Preventive Interventions for Early OHSS

OHSS will for each treatment group be tabulated by classification (mild, moderate, severe, moderate or severe) and grade (1, 2, 3, 4, 5). Early OHSS is defined as OHSS with onset ≤ 9 days after triggering of final follicular maturation. Note this includes OHSS with onset before triggering and OHSS with onset during stimulation where triggering is not performed.

This endpoint will be tabulated and analysed in a similar manner as the proportion of subjects with cycle cancellation, i.e. using a logistic regression model with treatment and AMH stratum as fixed factors. Analyses will be performed for subjects with early OHSS, subjects with early OHSS of moderate or severe grade, subjects with preventive interventions for early OHSS, subjects with early OHSS and/or preventive interventions for early OHSS, and subjects with early OHSS of moderate or severe grade and/or preventive interventions for early OHSS. The difference between treatments will be reported as an odds ratio including a 95% confidence interval and a p-value for the test of no difference between treatments.

The risk of preventive interventions for early OHSS and/or early OHSS is related to the ovarian response potential. AMH is a well-established predictor of ovarian response to gonadotropin treatment and was confirmed to be the best endocrine marker of ovarian response to FE 999049 treatment in the phase 2 trial. Since FE 999049 is dosed based on AMH it is likely that the relationship between AMH and the risk of experiencing preventive interventions for early OHSS and/or early OHSS differs between FE 999049 and FOLLISTIM. To further explore this for each of the endpoints above, two different logistic regression models will be fitted assuming an increasing risk with increasing AMH with two nested models as follows:

Model 1: $\text{LOGIT}(\pi) = \beta_0 + \beta_1 \cdot \ln(\text{AMH})$,

where π denotes the risk and the β 's denotes the regression coefficients.

Model 2: $\text{LOGIT}(\pi) = \beta_0 + \beta_1 \cdot \ln(\text{AMH}) + \beta_{2,i} + \beta_{3,i} \cdot \ln(\text{AMH})$, where $i=1, 2$ indicates the two treatments. This is model 1 with addition of treatment and treatment-by- $\ln(\text{AMH})$ interaction terms.

The two models will be compared using the likelihood ratio test. Adjusted odds ratio estimates (comparing FE 999049 to FOLLISTIM) and associated 95% Wald CI will be provided. A statistically significant improvement with model 2 compared to model 1 should be interpreted as a treatment difference in that the relationship between AMH and the risk of experiencing preventive interventions for early OHSS and/or early OHSS.

The estimated risks based on the models will be plotted as a function of AMH, i.e. overall and for each treatment group. The plots will include observed incidences for AMH-based subgroups of

subjects. The adequacy of the model fits will be evaluated using the Hosmer-Lemeshow goodness-of-fit test and by examining how well the model fit describes the data in the plot.

It can be noted that the likelihood ratio test using two nested models above corresponds to a test of the contrast $\beta_{2,1} = \beta_{2,2} = \beta_{3,1} = \beta_{3,2} = 0$ in model 2 above.

Late OHSS (Including OHSS of Moderate/Severe Grade)

OHSS will for each treatment group be tabulated by classification (mild, moderate, severe, moderate and severe) and grade (1, 2, 3, 4, 5). Late OHSS is defined as OHSS with onset >9 days after triggering of final follicular maturation.

This endpoint will be tabulated and analysed in a similar manner as the proportion of subjects with early OHSS. The analysis will be performed for subjects with late OHSS, and subjects with late OHSS of moderate or severe grade.

OHSS (Early and/or Late) and/or Preventive Interventions for Early OHSS

This endpoint will be tabulated and analysed in a similar manner as the proportion of subjects with early OHSS and/or preventive interventions for early OHSS. Analyses will be performed for subjects with early and/or late OHSS, subjects with early and/or late OHSS of moderate or severe grade, subjects with early and/or late OHSS and/or preventive interventions for early OHSS, and subjects with early and/or late OHSS of moderate or severe grade and/or preventive interventions for early OHSS.

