| IU | international units |
| IVF | in vitro fertilisation |
| J-GCP | Japanese Good Clinical Practice |
| J-NDA | Japanese New Drug Application |
| JSOG | Japan Society of Obstetrics and Gynaecology |
| L | Litre |
| LH | luteinising hormone |
| LLOQ | lower limit of quantification |
| LPLV | last patient last visit |
| MedDRA | Medical Dictionary for Regulatory Activities |
| mL | millilitre |
| NCU | neonatal care unit |
| NICU | neonatal intensive care unit |
| NIMP | non-investigational medicinal product |
| OHSS | ovarian hyperstimulation syndrome |
| OR | oocyte retrieval |
| PER.C6 [®] | name of cell line of human fetal retinal origin |
| PD | pharmacodynamics |
| PK | pharmacokinetics |
| PMDA | Pharmaceuticals and Medical Devices Agency |
| pmol | picomol |
| PP | per-protocol |
| PT | preferred term |
| rFSH | recombinant follicle-stimulating hormone |
| SAE | serious adverse event |
| SAP | statistical analysis plan |
| SOC | system organ class |
| SUSAR | suspected unexpected serious adverse reaction |
| t _½ | elimination/terminal half-life |
| t _{max} | time to C _{max} |
| TSH | thyroid-stimulating hormone |

µg microgram
ULOQ upper limit of quantification
WHO World Health Organization

AMH Unit Conversion Factors

1 pmol/L = 0.140 ng/mL

1 ng/mL = 7.143 pmol/L

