A phase 1 trial (CS03) conducted in healthy female Japanese volunteers demonstrated a linear, dose-response relationship of FE 999049 with respect to exposure. Furthermore, comparisons between Japanese and Caucasian women indicated similar PK profile with respect to C_{max} , AUC, t_{max} and $t_{1/2}$.¹

Two randomised, controlled, assessor-blind, parallel groups, multi-centre phase 2 anti-Müllerian hormone (AMH)-stratified trials were conducted in IVF/ICSI patients, one in Europe (000009)² and one in Japan (000124)³, with the purpose of determining the dose-response relationship of FE 999049 and the number of oocytes retrieved. In both trials, randomisation was stratified according to AMH levels at screening; low AMH (5.0-14.9 pmol/L) or high AMH (15.0-44.9 pmol/L).^a

In the European dose-response phase 2 trial (000009), five doses of FE 999049 ranging from 5.2 $\mu\text{g}/\text{day}$ to 12.1 $\mu\text{g}/\text{day}$ were investigated and a reference group of an approved rFSH product (GONAL-F, 150 IU/day) was also included. In the Japanese dose-response phase 2 trial (000124), three doses of FE 999049 (6 $\mu\text{g}/\text{day}$, 9 $\mu\text{g}/\text{day}$ and 12 $\mu\text{g}/\text{day}$) were investigated and a standard therapy of the approved rFSH product (FOLLISTIM, 150 IU/day) was also included. At present, follitropin beta (FOLLISTIM) is the only medicinal product approved in Japan for controlled ovarian stimulation in IVF/ICSI cycles. In the European and the Japanese phase 2 trials, the daily dose was fixed throughout the stimulation period. In both trials, a statistically significant dose-response relationship for FE 999049 with respect to the number of oocytes retrieved was observed for the overall population and for each AMH randomisation stratum. Acceptable pregnancy rates were achieved with all FE 999049 doses. Furthermore, the observed FE 999049 dose-response profile was similar in the European trial and in the Japanese trial.

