The risk of preventive interventions for early OHSS and/or early OHSS is related to the ovarian response potential. AMH is a well-established predictor of ovarian response to gonadotropin treatment and was confirmed to be the best endocrine marker of ovarian response to FE 999049 treatment in the phase 2 trial.

For each endpoint two different logistic regression models will be fitted assuming an increasing risk with increasing AMH as follows:

$$\text{LOGIT}(\pi) = \beta_0 + \beta_1 \log(\text{AMH}),$$

where π denotes the risk and the β 's denotes the regression coefficients.

A comparison of the two treatment regimens with respect to the risk will be performed by adding treatment group as factor and the interaction term between treatment group and $\log(\text{AMH})$ to the model as follows:

$$\text{LOGIT}(\pi) = \beta_0 + \beta_1 \text{Treatment} + \beta_2 \log(\text{AMH}) + \beta_3 \text{Treatment} * \log(\text{AMH})$$

The two models will be compared using the likelihood ratio test. Adjusted odds ratio estimates (comparing FE 999049 to FOLLISTIM) and associated 95% Wald CI will be provided.

The adequacy of the model fits will be evaluated using the Hosmer-Lemeshow goodness-of-fit test. The estimated risks based on the models will be plotted as a function of AMH, i.e. overall and for each treatment group.

Late OHSS (Including OHSS of Moderate/Severe Grade)

OHSS will for each treatment group be tabulated by classification (mild, moderate, severe, moderate and severe) and grade (1, 2, 3, 4, 5). Late OHSS is defined as OHSS with onset > 9 days after triggering of final follicular maturation.

This endpoint will be tabulated and analysed in a similar manner as the proportion of subjects with early OHSS. The analysis will be performed for subjects with late OHSS, and subjects with late OHSS of moderate or severe grade.

OHSS (Early and/or Late) and/or Preventive Interventions for Early OHSS

This endpoint will be tabulated and analysed in a similar manner as the proportion of subjects with early OHSS and/or preventive interventions for early OHSS. Analyses will be performed for subjects with early and/or late OHSS, subjects with early and/or late OHSS of moderate or severe grade, subjects with early and/or late OHSS and/or preventive interventions for early OHSS, and subjects with early and/or late OHSS of moderate or severe grade and/or preventive interventions for early OHSS.

Number and Size of Follicles during Stimulation

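### Does SAP 10.3 need to name the AMH value at which its exploratory OHSS odds ratios are evaluated?

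*SAP*

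**What the plan says.** SAP 10.3 sets out two layers of analysis for the OHSS endpoints.

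- **Summary comparison.** A logistic model with treatment and AMH stratum. "The difference between treatments will be reported as an odds ratio including a 95% confidence interval and a p-value", and this model has no interaction term.
- **Exploration by AMH.** Because the FE 999049 dose depends on AMH, the SAP considers that "it is likely that the relationship between AMH and the risk of experiencing preventive interventions" for early OHSS, or early OHSS itself, differs between the products. Model 1 regresses the logit of risk on ln(AMH). Model 2 adds treatment and treatment-by-ln(AMH). The two are compared by a likelihood ratio test, and a significant gain is to be read as a treatment difference in the AMH-risk relationship. The next promise is: "Adjusted odds ratio estimates (comparing FE 999049 to FOLLISTIM) and associated 95% Wald CI will be provided". Also, "The estimated risks based on the models will be plotted as a function of AMH", with observed incidences for AMH subgroups added to the plots.

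Protocol 9.7.4 builds the same larger model "by adding treatment group as factor and the interaction term between treatment group and" log(AMH). Neither document names an AMH value for the odds ratio. SAP section 14 places the table shells in a separate document, which is not available here.

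**The concern.** With an interaction in the model there is no single treatment odds ratio; there is one for every AMH value. If the treatment coefficient alone were exponentiated under reference coding, the result would be the odds ratio where ln(AMH) = 0, that is at 1 pmol/L. The phase 2 strata in Protocol 1.1 ran from 5.0 to 44.9 pmol/L, so that could be a far extrapolation.

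The Protocol's list of AMH conversion factors also gives "1 ng/mL = 7.143 pmol/L", so the same coefficient with AMH in ng/mL would refer to 7.143 pmol/L. Under sum-to-zero coding it would be half the log odds ratio.

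At stake would be an AMH-specific estimate on what Protocol 1.1 calls the most serious risk of gonadotropin treatment, repeated over 11 OHSS analyses (5 early, 2 late, 4 combined). The SAP's note on the test ("It can be noted that the likelihood ratio test using two nested models above corresponds to a test of the contrast") adds to the unease, because it sets four terms to zero where two equalities define the null.

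**Working it through.** The documents give no figure for this odds ratio, so there is nothing to reproduce. The check is algebra plus an illustration.

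**1. What is estimated.** Model 1 has no treatment term, so the odds ratio comes from Model 2. Write τ = β2,FE − β2,FO and δ = β3,FE − β3,FO. Then ln OR(a) = τ + δ·ln(a) at AMH = a.

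**2. Unit.** Multiply AMH by a constant c. The intercept difference becomes τ − δ·ln(c), and (τ − δ·ln c) + δ·ln(c·a) = τ + δ·ln(a). At a named AMH the odds ratio is unchanged. The SAP uses only pmol/L for AMH (sections 3.1 and 4), as do the dosing table and the strata in the Protocol.

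**3. Coding.** τ and δ are differences between treatments and do not depend on the coding. Under ±1 coding the printed coefficient is τ/2. Its exponential is the square root of the odds ratio, which is not a comparison of FE 999049 to FOLLISTIM as the SAP requires. Reporting it would be a programming error.

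**4. Size of the choice of AMH.**
- From the documents: 328 randomised (SAP 3.2), so 164 per arm; 19.5% early moderate/severe OHSS on FOLLISTIM in the Japanese phase 2 trial (Protocol 1.1).
- Assumed: that 19.5% applies at AMH 20 pmol/L; odds ratio 0.50 at AMH 20; δ = −0.4; ln(AMH) normal with median 18 and SD 0.7; FOLLISTIM slope 1.0 per ln unit.
- Formulas: OR(a) = 0.50 × (a/20)^δ; 95% CI = exp(ln OR ± 1.96·SE), with SE from the expected information of the four-parameter model.
- Assumed quartiles: 18 × exp(±0.6745 × 0.7) = 11.2 and 28.9.

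| AMH (pmol/L) | OR | SE of ln OR | 95% CI |
|---|---|---|---|
| 1 | 0.50 × (1/20)^−0.4 = 1.66 | 1.55 | 0.08 to 34 |
| 7.143 | 0.75 | 0.65 | 0.21 to 2.69 |
| 11.2 (25th percentile) | 0.63 | 0.47 | 0.25 to 1.59 |
| 15 | 0.56 | 0.38 | 0.27 to 1.19 |
| 18 (median) | 0.52 | 0.34 | 0.27 to 1.02 |
| 20 | 0.50 | 0.33 | 0.26 to 0.96 |
| 28.9 (75th percentile) | 0.43 | 0.34 | 0.22 to 0.85 |

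For δ from 0 to −0.8, the odds ratio at 15 pmol/L runs only from 0.50 to 0.63; at 1 pmol/L it runs from 0.50 to 5.49.

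**5. The likelihood ratio test.** The Protocol's version adds one treatment and one interaction coefficient to the smaller model, so the test has 2 degrees of freedom. In the SAP's notation, either usual identifying constraint (reference level zero, or sum to zero) makes the four zeros the same two restrictions as β2,1 = β2,2 and β3,1 = β3,2. In one simulated dataset the statistic was 24.95 under reference coding in pmol/L, sum-to-zero coding, and reference coding in ng/mL. The contrast wording is therefore a clerical matter.

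**The case for a change.** The strongest case for a change is that a SAP exists to remove choices made after seeing data, and the plan itself expects an interaction here. In the illustration the interval excludes 1 at 20 and 28.9 pmol/L but not at 15 or 18, so the choice of AMH could colour a sentence in the report. The planned plots show risks, not odds ratios with intervals. In simulated trials under the same AMH assumptions, the estimates at 1 and 20 pmol/L fell on opposite sides of 1 in 32% of trials with no interaction, 62% at δ = −0.4 and 85% at δ = −0.8.

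Some of this stands: the evaluation point is unstated, and one sentence would have been tidy. The rest carries less weight.

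- The simulated percentages all require reporting at 1 pmol/L, which no section asks for. The 32% with no interaction reflects imprecision there (SE about 1.6), not an ambiguous effect.
- The phase 2 range is not this trial's range. Protocol 4.1 sets no AMH limit and both strata are open-ended.
- An interval that excludes 1 at some AMH values and not others is what any interaction model shows. Naming values in advance would not remove it. Four values over 11 analyses would give 44 odds ratios, with no multiplicity adjustment (SAP 9.1).
- An out-of-range odds ratio would be plainly at odds with the risk curves and the observed subgroup incidences on the same plots.

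A related gap is which AMH enters the model, since it is measured at screening and on stimulation day 1 (Protocol 7.3.14 and 7.4.9). The rationale in SAP 10.3 is AMH-based dosing, and dosing and strata both use the screening value, so that is the natural choice.

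**Conclusion.** No change is needed. The plan leaves out a reporting detail of an exploratory secondary safety analysis; it states no rule that gives a wrong result. The nested test, the stratum-adjusted odds ratio with its interval and p-value, and the risk curves by AMH are all defined and unaffected, as is the primary endpoint. A competent analyst would evaluate the Model 2 odds ratio at AMH values typical of the trial, in pmol/L, with intervals from the joint covariance of the treatment and interaction terms. The table shells may already say so.

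In the illustration that choice moves the estimate from 0.63 to 0.43 across the middle half of the AMH distribution, always in the same direction. The AMH distribution, the slopes and the odds ratio of 0.50 are assumptions, and the figures do not predict the trial's result. A report that presented a bare Model 2 coefficient as the treatment effect should be queried then, as an error of execution.
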